2.3 Clinical manifestations

The clinical manifestations of COVID-19 are nonspecific, may remain asymptomatic, mild clinical manifestations such as fever, cough, sore throat, fatigue, dyspnea, myalgia, headache, vomiting and diarrhea (14,20). Presentation and severity usually vary by age (> 65 years), comorbidities and compromised immune system. In these cases the patient may be at increased risk of developing organ dysfunction, including shock, acute respiratory distress syndrome (ARDS), acute cardiac injury, and acute kidney injury, resulting in a higher mortality rate (15). Symptoms of COVID-19 infection appear after an incubation period of 5-6 days, the time period between symptom onset and death ranges from 6 to 41 days, with a median of 14 days. The median time from symptom onset to dyspnea is 5 days, hospitalization 7 days and the onset of ARDS is 8 days. The need for admission to the Intensive Care Unit (ICU) in several published series is 25 - 30%. Different complications have been evidenced, which include (21):

2.3.1 Pulmonary damage: in severe cases of COVID-19 there is a decreased ratio between arterial oxygen partial pressure and fractional inspired oxygen (PaO₂: FiO₂ ratio) with concomitant hypoxia and tachypnea. In addition, low CO₂ levels have been observed as the mean partial pressure of carbon dioxide (PaCO₂) level at 34 mmHg. In summary, hypoxia and hypercapnia are observed in severe cases. (22). IL-6 acts as a potent proinflammatory factor and has been implicated as a strong predictor of respiratory failure (23).

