3. JUSTIFICATION

COVID-19 is a disease that spreads rapidly and has a high mortality rate, which has caused the collapse of health systems; therefore, it is important to implement a comprehensive treatment to avoid complications of the disease, reduce the length of hospital stay and provide a rapid recovery. Treatment costs can vary from \$500,000 Mexican pesos per admission to \$1,512,000

pesos, considering an average hospital stay of 12 days (5). It has been seen that 26.4% of hospitalized patients recovered and were discharged from the hospital, and 46.4% improved and were reclassified. 13.4% have died (6). There are several lines of treatment, but nutrition is only considered within the caloric intake. In this study a nutritional therapy called NSS will be evaluated, trying to reduce complications in patients with COVID-19, as well as reduction of hospital stay days, disease progression, percentage of progression to mechanical ventilation and mortality. This study will provide scientific evidence to establish new strategies to improve the clinical evolution of patients with COVID-19 worldwide. This study is feasible given that it has the material and human resources to be carried out and is pertinent given that it seeks to contribute to the study of new nutritional therapies to reduce complications and mortality in patients with COVID-19.

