6. HYPOTHESIS

The nutritional support system will reduce complications in patients with COVID-19 and comorbidities (type 2 DM, HAS, overweight/obese with BMI <35) in stage III, with a better benefit than that achieved with conventional nutritional treatment.

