7. GENERAL OBJECTIVE

To determine the effect of the use of a nutritional support system on complications in patients with COVID-19 and comorbidities (type 2 DM, HAS, overweight/obesity with BMI <35) in stage III, compared with conventional nutritional treatment.

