7.1. SPECIFIC OBJECTIVES

1. To correlate biochemical and inflammatory factors with the evolution of the study groups.
2. To correlate body composition with the clinical evolution of the patients.
3. To evaluate the days of hospital stay, disease progression, percentage of progression to ventilator and mortality as predictive indexes of patient improvement.
4. To stratify in groups by age ranges (30-39, 40-49, 50-59 and >60 years).

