The energy balance of the supplements will be considered within the designated caloric balance for this group. The follow-up will be performed daily for 21 days or earlier, if they are discharged from hospital due to improvement in evolution or require access to the ICU, at which time the patient concludes the study. The following points will be supervised: 1. Application and consumption of the NSS supplementation as appropriate. 2. Recording of all the information in the records. 3. Food diaries of each patient. 4. Laboratory studies: QS every other day, BH every 3rd day, coagulation times every 3rd day, D-dimer and fibrinogen every 3rd day, serum electrolytes every other day, serum homocysteine every other day and serum 25 hydroxycholecalciferol levels every other day. 5. SpO2 %, heart rate, respiratory rate. 6. Clinical evaluation and record of bowel movements. 7. Taking of tricipital fold and arm

circumference, % muscle mass, % fat, BMI, weight, height every two days. 8. Days of hospital stay.

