A handwritten signature in black ink, appearing to be '[name]', written over a horizontal line. The signature is stylized with loops and a long vertical stroke at the end.

6. Roles and Responsibility - signatures

Names	Roles and Responsibility	Signature
[name] M.D., MSc., DSc.	Conceptualization, formal analysis, funding acquisition, investigation, methodology, project administration, supervision, writing-review, and editing.	
[name] M.D., MSc., DSc.	Formal analysis, funding acquisition, review, and editing.	
[name] M.D.	Data curation, formal analysis, investigation, methodology, project administration resources, writing-review, and editing.	
[name] M.D.	Data curation, formal analysis, investigation, methodology, project administration resources, writing-review, and editing.	
[name] M.D.	Data curation, investigation, methodology, project administration resources, writing-review, and editing.	

[name]	Data curation, formal analysis, investigation, methodology, writing-review, and editing.	
[name] M.D	Hospital Resources.	

Section 2: INTRODUCTION

7. Background and rationale of study (optional)

Item 7: Synopsis of trial background and rationale including brief description of research question and brief justification for undertaking the trial

COVID-19 is a rapidly spreading disease with a high hospital mortality rate. It has caused the collapse of health systems worldwide due to the lack of specific treatments to reduce complications and mortality. Nutrition has only been considered as an energetic support even though malnutrition has been associated with a higher risk of mortality. Therefore, it is important to investigate a nutritional support system that helps to reduce mortality and increase survival in patients with COVID-19 in stage III and comorbidities to a greater degree than with conventional nutritional treatment.

8. Objectives and hypotheses.

Item 8: Description of specific objectives or hypotheses

The primary objective is to determine the effectiveness of the Nutritional Support System (NSS) on increasing survival and reducing mortality in patients with COVID-19 in stage III and comorbidities compared to conventional nutritional therapy.

Secondary objectives:

1. To evaluate the effect of the NSS on progression to intubation, evolution to extubation, and mortality in intubated patients.

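### SAP Item 8 ranks the two intubation outcomes as secondary, Items 26a and 27 rank them as primary, and the promotion of mortality over the protocol's undefined complications aim is neither explained nor dated in the text available

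*SAP*

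**What the plan says.** **Protocol.** The hypothesis (section 6) is that "The nutritional support system will reduce complications in patients with COVID-19 and comorbidities". The general objective (section 7) is "To determine the effect of the use of a nutritional support system on complications in patients with COVID-19 and comorbidities". The research question (section 5) has the same target. No primary outcome is named, and complications have no outcome definition, list of qualifying events or time point. Section 2.3 lists organ-system complications, but as disease background. Mortality does appear. The Justification adds, beside complications, "as well as reduction of hospital stay days, disease progression, percentage of progression to mechanical ventilation and mortality", and specific objective 3 (section 7.1) begins "To evaluate the days of hospital stay, disease progression, percentage of progression to ventilator and mortality".

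**SAP objectives and framework.** Item 8: "The primary objective is to determine the effectiveness of the Nutritional Support System (NSS) on increasing survival and reducing mortality". The null and research hypotheses are both about mortality and survival, and Item 12 ties superiority to the same effect. Secondary objective 1 in Item 8 is "To evaluate the effect of the NSS on progression to intubation, evolution to extubation, and mortality in intubated patients".

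**SAP outcomes and analysis.** Item 26a has three entries under its primary heading: overall mortality and survival, progression to ventilation, and mortality and survival in intubated patients. The Item 27 table marks all three as primary, each with Kaplan-Meier and log-rank. Item 17 says no multiplicity procedure is required. Item 16 makes p-values one-sided, with 0.05 as the limit.

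**Results in the same file.** The legends to Figures 2 and 3 give counts by arm for a follow-up running from September 2020 to April 2021. A log-rank p-value is printed for overall survival only.

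**The concern.** Two outcomes have two ranks. Read from Item 8, the trial has one primary outcome; read from Items 26a and 27, it has three, each tested at 0.05 with no adjustment. That decides whether the survival p-value is the single planned test or one of three.

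The origin of the survival outcome is also undocumented in the text available. The protocol's general aim was complications. The SAP's is mortality, and the file that sets the ranking also holds the deaths by arm. If the ranking or the promotion was settled with those deaths in view, p=0.027 cannot carry a confirmatory claim. If it was settled beforehand, a dated statement would show that.

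Finally, two planned log-rank results are not printed. The legend to Figure 3 gives only the decreases of 10% and 38.1%, with no p-value and no interval for either difference.

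**Working it through.** **1. Rank of each outcome in the SAP**

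| Outcome | Item 8 | Item 12 and hypotheses | Item 26a | Item 27 |
|---|---|---|---|---|
| Overall survival/mortality | primary | named | primary | primary |
| Progression to intubation | secondary | not named | primary | primary |
| Mortality in intubated patients | secondary | not named | primary | primary |

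With three unadjusted tests at 0.05, the chance of at least one false positive would be 1 − 0.95³ = 0.143 if the tests were independent. They are not (deaths after intubation count in two of them), so this is only an illustration.

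**2. Time origin.** Items 14 and 15 start mortality in ventilated patients at intubation. Item 26a starts it at baseline.

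**3. Effect sizes** from the counts in the legends to Figures 2 and 3, control minus intervention, with Newcombe 95% intervals:

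| Outcome | Counts | Difference (points) | 95% interval | Fisher two-sided / one-sided | Printed log-rank p |
|---|---|---|---|---|---|
| Death | 7/40 v 1/40 | 15.0 | 1.4 to 29.6 | 0.057 / 0.028 | 0.027 |
| Ventilation | 7/40 v 3/40 | 10.0 | −5.1 to 25.3 | 0.311 / 0.155 | none |
| Death in intubated | 5/7 v 1/3 | 38.1 | −20.0 to 72.1 | 0.500 / 0.333 | none |

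**4. The two missing log-rank results.** Event times are not printed, so the statistic was computed over every order of untied events. At each event, with n₁ control and n₀ intervention patients at risk, E = n₁/(n₁+n₀) and V = n₁n₀/(n₁+n₀)²; z = (O − ΣE)/√ΣV, where O is the number of control events. Assumption: nobody is censored early. The exception is the 7 − 5 = 2 control deaths without ventilation, which may leave the ventilation analysis at any time.

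- *Check on the printed figure.* Overall deaths give 0.024 to 0.029 two-sided. The printed 0.027 lies inside, so it appears to be two-sided although Item 16 says one-sided.
- *Ventilation.* The smallest p arises when the two control deaths come first (38 v 40 at risk) and the seven control events precede the three intervention events: ΣE = 4.593, ΣV = 2.481, z = (7 − 4.593)/1.575 = 1.528, one-sided 0.063. Over all orders: 0.126 to 0.210 two-sided.
- *Death in intubated.* The smallest p arises when all five control deaths precede the intervention death: ΣE = 7/10 + 6/9 + 5/8 + 4/7 + 3/6 + 2/5 = 3.463, ΣV = 1.402, z = (5 − 3.463)/1.184 = 1.298, one-sided 0.097. Over all orders: 0.194 to 0.477 two-sided.

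Random draws with tied days raise the two upper ends to 0.212 and 0.525 and leave the lower ends unchanged.

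**5. Is the censoring assumption safe?** Not fully. Figure 3-B prints a mean of 26.66 for the three intubated intervention patients, one of whom died. If both survivors were followed for 40 days, the death falls at 3 × 26.66 − 2 × 40 = −0.02, that is, day 0. Earlier censoring of survivors is the more plausible explanation. The means in Figure 3-A also lie near day 10. With arbitrary early censoring, some extreme ventilation patterns fall below 0.05 one-sided.

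**6. Timing.** Item 14 speaks of a September 2020 start in the future tense, while the figure legends report results to April 2021. The SAP text available begins at Item 6. Protocol section 8.4 ends follow-up at 21 days, discharge or ICU entry, so survival to day 40 also needs follow-up beyond what the protocol describes.

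**The case against.** The strongest reply is that the SAP has one confirmatory hypothesis and some careless labels. Item 8, both hypotheses and Item 12 all name survival/mortality, and overall survival comes first in Items 26a and 27. That stands, and it makes one primary outcome the likelier reading. It does not remove the contradiction, because Items 26a and 27 are where the outcomes and tests are specified.

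A reader might infer that mortality was brought in after the deaths were seen. The documents do not support that. Mortality is in the protocol's Justification and specific objective 3, so the SAP promotes a named outcome. Item 14 reads as written beforehand, and opening SAP pages not available here may hold a date or a reason. Printed results in the file show only that the order of events is unsettled.

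A reader might also infer that the two unprinted tests failed and were left out for that reason. The counts make significance unlikely, but the log-rank ranges rest on a censoring assumption that Figure 3-B puts in doubt, and no document says why the p-values are absent.

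**Conclusion.** The point holds as an internal contradiction with an undocumented promotion. It is not evidence of outcome switching.

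- Two outcomes are secondary in Item 8 and primary in Items 26a and 27, with no multiplicity control. This rests on the text alone.
- The promotion of mortality over the general complications aim is unexplained in the text available, and whether it came before the data cannot be settled from it.
- Survival is the only one of the three outcomes with a printed p-value (0.027). The intervals for the other two include zero: −5.1 to 25.3 and −20.0 to 72.1 points. Their smallest one-sided log-rank values are about 0.063 and 0.097, given no early censoring apart from the two control deaths without ventilation; actual censoring could change them.
- The 7 v 3 comparison of deaths is in a subgroup formed after randomisation, so it cannot be read as a randomised comparison at any rank.

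Of minor weight: length of stay, which is in specific objective 3 and is a supervised item in Protocol 8.4 ("Days of hospital stay"), and evolution to extubation, which is in Item 8, have no row in Item 27. Specific objective 3 calls its items predictive indexes, so the status of length of stay as an efficacy outcome is itself unclear.

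**What to change.** 1. **One rank.** Make Items 26a and 27 agree with Items 8 and 12: overall survival as the single primary outcome and both intubation outcomes secondary, unless a dated earlier document shows otherwise. If the ranking was settled after arm results were printed, say so.
2. **Report both intubation comparisons** with estimate, interval and log-rank p-value whatever their rank. First reconcile the time origin for mortality in intubated patients (Items 14 and 15 v Item 26a) and state how survivors were censored. Label that comparison descriptive.
3. **Document the promotion.** State in Item 8 that survival/mortality was raised from specific objective 3 in place of the general complications aim, when, and whether deaths by arm were then known. If precedence cannot be shown, label the mortality p-value non-confirmatory.
4. **Minor.** Add rows for length of stay and evolution to extubation, covering all relevant randomised patients with death as a competing event or worst rank, or report them as not analysed and give the reason.

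Cost: wording in Items 8, 26a and 27, and two log-rank results from data already held. Some chart retrieval may be needed for the minor items. The downside is a softer mortality claim if precedence cannot be shown, and two reported comparisons that may not reach significance.

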1. ABSTRACT

The disease caused by SARS-CoV-2 has become a pandemic in which its evolution and complications depend on the immunological capacity of the host. In Mexico, the global lethality rate of the virus is 11.3% (1,2), with a mortality rate of 0.2795 per 1000 inhabitants (3). It is relevant to study therapies that allow the host to recover and reduce complications; to date, the virus has been characterized by an inflammatory cascade, increased by the overproduction of cytokines, the decrease of metalloenzymes and the rapid dissemination of the virus. There are several lines of treatment, however, nutrition is considered as a caloric contribution and not as part of the treatment. For this reason, this study will evaluate the evolution of patients with COVID-19 assisted by a nutritional support system (NSS) based on supplements such as omega 3, zinc, selenium, vitamin D, glutamine, arginine, magnesium, cobalamin, pyridoxine, thiamine, prebiotics, probiotics, foods such as Spirulina Maxima, brewer's yeast and the effect of this therapy in the reduction of complications and comorbidities. Research question: Will the nutritional support system reduce complications in stage III COVID-19 patients with comorbidities (type 2 DM, HAS, overweight/obesity with BMI <35) with a better benefit than that achieved with conventional nutritional therapy? Hypothesis: The nutritional support system will reduce complications in patients with COVID-19 with stage III comorbidities. General Objective: To determine the effect of the use of a nutritional support system on complications in patients with COVID-19 and stage III comorbidities. Methodology: A controlled, blinded and randomized clinical trial will be conducted in patients with COVID-19, both sexes, older than 30 years old, hospitalized at Centro Médico ISSEMYM Toluca Arturo Montiel Rojas, who meet the inclusion criteria and are classified in stage III. Two groups will be evaluated: 1. Control group (CG) which will receive the normal diet implemented by the hospital and 2. Intervention group (IG) which will receive the normal diet implemented by the hospital together with the NSS. Blood chemistry of 46 elements, coagulation tests, blood biometry, % SpO₂, homocysteine, 25-hydroxycholecalciferol, clinical data and anthropometry will be evaluated at baseline and during their hospital stay.

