8. METHODOLOGY

8.1 Type of study and overall design: Blinded, randomized controlled clinical trial.

8.2 Study Universe.

Patients diagnosed with COVID-19 by PCR test, who are attended at Centro Medico ISSEMYM Toluca Arturo Montiel Rojas, located at [name]; both sexes, with presence of comorbidities and in stage III.

8.3 Selection and sample size: the sample size will be calculated using the formula: $n = \frac{z^2 pq}{e^2}$, where: 95% confidence level ($z = 1.96$), $p = 0.975$, $q = 0.025$, with a margin of error of 5% ($e = 0.05$), obtaining 38 patients per group for the sample.

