2. To evaluate the effect of NSS on clinical and biochemical changes among patients.
3. To evaluate the effect of NSS on the biochemical status associated with overall mortality.

Study hypotheses

The null hypothesis: The nutritional support system will not reduce mortality or increase survival in patients with COVID-19 in stage III and comorbidities compared to conventional nutritional therapy.

Research hypothesis: The nutritional support system will reduce mortality and increase survival in patients with COVID-19 in stage III and comorbidities compared to conventional nutritional treatment.

Section 3: Trial Methods

9. Trial design - description of trial design

Item 9: Brief description of trial design including type of trial

Randomized, blinded, controlled clinical trial. Selected patients will be randomized into two groups: 1) Control Group (CG) will receive the hospital diet and 2) Intervention Group (IG) will receive the hospital diet and the NSS. Treatment allocation will have a 1:1 ratio.

10. Randomization

Randomization will be performed using a raffle; eighty numbers are to be placed (from 1 to 80). Subsequently, each number will be randomly selected from the raffle and sequentially assigned to one of the two groups, until reaching 40 numbers per group. Each number represents the moment the patient enrolls. In this way, once the recruitment starts, the first patient will be assigned number one; the second will be number two, and so on.

11. Sample size

Item 11: Full details of the same size calculation or alternatively reference to sample size calculation in protocol (instead of replication in SAP).

The sample size will be calculated using the formula: $n = \frac{z^2 p q}{e^2}$, where: 95% confidence level ($z = 1.96$), $p = 0.975$, $q = 0.025$, with a margin of error of 5% ($e = 0.05$), obtaining 38 patients per group for the sample.

12. Framework

Item 12: Superiority, equivalence or non-inferiority trial hypothesis testing framework, and wick comparisons will be presented on this basis.

The effect of NSS in increasing survival and reducing mortality in patients with COVID-19 will be demonstrated by the significant superiority of IG over CG.

13. Statistical Interim analyses and stopping guidance

Item 13a: Information on interim analyses specifying what interim analyses will be carried out and listing of time points:

No interim analyses are planned in the study.

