- SpO2 without supplemental oxygen, use of home oxygen upon hospital discharge, days of supplemental oxygen use, post-covid syndrome, decrease in body weight: all will be analyzed from hospital discharge until day 40.

Section 4: Statistical Principles

16. Confidence intervals and p-values

Item 16: Level of statistical significance

P values ≤ 0.05 will be considered indicative of statistical significance in all cases. P values will be one-sided.

Item 17: Description of any planned adjustment for multiplicity, and if so, including how the type I error is to be controlled

This study will not analyze data that required multiplicity tests. To avoid type 1 error, an alpha value of 5% will be used (considering $p < 0.05$ significant), aberrant data will be eliminated, validated tests applicable to the study variables will be defined and established, specific inclusion criteria will be implemented for homogenization of the sample to avoid bias variables, and a specific sample size calculation will be performed.

Item 18: Confidence intervals (CI) to be reported

All the confidence intervals presented will be 95%.

19. Adherence and Protocol Deviations

Item 19a: Definition of adherence to the intervention and how this is assessed including extent of exposure.

The intervention will consist of: 1) 2 envelopes of NSS taken in a period of less than 15 minutes (without the presence of vomiting) after morning and afternoon meals during the first 21 days or until hospital discharge, 2) 1 capsule of *Saccharomyces Boulardii* before the NSS and 1 capsule with the second envelope for 6 days or until hospital discharge, 3) intramuscular B complex; 1 ampoule after meals for 5 days or at hospital discharge.

Adherence to treatment will be established as taking more than 95% of the NSS and not fasting for 2 consecutive days.

Item 19b: Description of how adherence to the intervention will be presented

The intervention will be applied by the research team, who will be responsible for the application and collection of data, which will be reported in daily formats in the morning and afternoon shifts.

The clinical investigators are going to prepare each supplement, administer, and witness each intake of the NSS, registering the time as well as any immediate side effects such as vomiting, bloating, and abdominal pain.

Item 19c: Definition of protocol deviation for the trial:

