- Not meeting inclusion criteria including patients with respiratory rate disturbance (>30 bpm), glycemia >250 mg/dl, Glomerular filtration rate (GFR) < 60 ml/kg/m², platelets level (<150 10³ /L), concomitant autoimmune diseases (hypothyroidism, rheumatoid arthritis, atopic dermatitis), and/or respiratory disorders (bronchial asthma, obstructive sleep apnea syndrome, chronic lung lesions).
- Declined to participate.
- Randomization of all patients.
- Assignment of 40 patients to CG (received hospital diet and hospital treatment) and 40 patients to IG (received intervention - NSS, probiotics, B complex, hospital diet, and hospital treatment).

- Report of incidents.
- Variables analyzed in both groups with their evaluation periods.
- Primary outcomes.

24. Withdrawal/ Follow-up - level of withdrawal

Item 24a: Level of withdrawal e.g. from intervention and/or from follow up

The withdrawal levels that could be present in the study are listed as follows:

1. Participants can withdraw from the intervention and follow-up stops but the information collected is considered as data.
2. If patients decide to withdraw from follow-up, they are asked to allow us to use the data collected to date.
3. If a patient does not allow his/her data to be analyzed, they will not be considered in the analysis.
4. If the patient presents secondary reactions or does not adequately follow the treatment, they should leave the study and their data will be considered for the analysis.
5. Data from patients who die will be considered in the analysis.

Item 24b: Timing of withdrawal/lost to follow up data

The report of withdrawals and losses will be established in the CONSORT diagram, Kaplan-Meier curves, and primary outcomes section, where the timing of withdrawals will be mentioned, as well as the analysis and number of deaths.

Item 24c: Reasons and details of how withdrawal/lost to follow up data will be presented

Reasons for patients deciding to withdraw and deaths from COVID-19 complications will be presented on the CONSORT diagram, Kaplan-Meier curves, and in the primary outcomes section.

25. Baseline patient characteristics

Item 25a: List of baseline characteristics to be summarized

The clinical characteristics, demographic analysis and baseline values will be presented in tables. Details of the randomization will be mentioned in the methods section.

Item 25b: Details of how baseline characteristics will be descriptively summarized

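### The trial is labelled blinded three times, but as described neither patients nor the team that gives the NSS and collects data can be blinded, and no masking is specified for anyone else

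*SAP*

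**What the plan says.** Three places give the design label. The protocol abstract (section 1) says "A controlled, blinded and randomized clinical trial will be conducted in patients with COVID-19". Protocol section 8.1 says "Blinded, randomized controlled clinical trial". SAP Item 9 says "Randomized, blinded, controlled clinical trial". None of them names a blinded party or a procedure.

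On what the arms receive, SAP Item 9 states "Control Group (CG) will receive the hospital diet", and the CONSORT list in SAP Item 23 has "Assignment of 40 patients to CG (received hospital diet and hospital treatment". For the intervention arm, SAP Item 19a lists "2 envelopes of NSS taken in a period of less than 15 minutes", taken morning and afternoon, then *Saccharomyces boulardii* capsules, and then "intramuscular B complex; 1 ampoule after meals for 5 days or at hospital discharge". The Procedure section of the protocol adds that each sachet is mixed with 400 ml of water.

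On who does the work, SAP Item 19b makes the research team responsible both for applying the intervention and for collecting data. It continues: "The clinical investigators are going to prepare each supplement, administer, and witness each intake of the NSS". The same people record intake times and immediate side effects, among them bloating and abdominal pain.

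**The concern.** A reader who meets the word blinded, with nothing to qualify it, will assume that expectation had little room to influence care, reporting or scoring. In this trial one arm visibly receives products that the other does not, and the people handing them over also collect data. If the label stands, outcomes that depend on what a patient says, how staff judge a sign, or when staff change a treatment will be read as protected when they are not. One of these, progression to intubation, is a primary outcome. Several others supply most of the starred results that the SAP already displays.

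**Working it through.** The plan gives no figure for blinding, so the check consists of reading the texts side by side and counting the exposed outcomes.

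**Step 1: could a patient be blinded?**

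| Component | Intervention arm | Counterpart in controls |
|---|---|---|
| NSS sachets | Two a day, 400 ml of water with each, so 2 × 400 = 800 ml (protocol, Procedure; SAP Item 19a) | None described |
| Probiotic | Capsules for the first 6 days (both documents) | None described |
| B complex | Intramuscular, 5 days (both documents) | None described |
| Hospital diet | Yes | Yes |

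Neither document mentions a placebo, a sham injection or a matched sachet or capsule. A patient knows whether these were given, so blinding of patients is impossible as described.

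**Step 2: could the staff who give the NSS and collect data be blinded?** SAP Item 19b gives both tasks to the research team and has the clinical investigators prepare, give and watch each intake. They know the arm. The protocol's daily follow-up list puts NSS consumption, record keeping, SpO2 and clinical evaluation together and names no separate assessor.

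**Step 3: could anyone else be blinded?** The SAP roles table gives formal analysis to five people. Four of them also hold investigation, and three of those four also hold data curation. The fifth holds neither. No coded dataset, masked assessor, masked laboratory or unblinding procedure is described. Masking of an analyst or of laboratory staff is therefore neither specified nor ruled out.

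**Step 4: which outcomes are exposed?** From SAP Items 26a and 27:
- Primary: progression to intubation, which rests on a staff decision.
- Secondary: oxygen flow (staff titration); qSOFA, distension and Bristol scale (staff judgement or recording); defecations, PHQ-9 and post-COVID syndrome (wholly or partly patient report).

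Table 2-A stars seven results:

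| Starred result | Type of test | Exposed? |
|---|---|---|
| Oxygen flow | Within intervention arm | Yes |
| qSOFA | Within intervention arm | Yes |
| PHQ-9 | Within intervention arm | Yes |
| Defecations, day 3 | Between arms | Yes |
| Distension, day 3 | Between arms | Yes |
| Hydric balance, day 3 | Between arms | Not counted |
| Saturation without oxygen, day 40 | Between arms | No, instrument reading |

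Hydric balance is not counted because the arms differ by 456.6 − 123.4 = 333.2 mL while only the intervention regimen specifies 800 ml a day of water with the sachets. The regimen itself could produce that difference without any effect of expectation. The exposed count is 7 − 1 − 1 = 5. Three of the five are within-group tests, which leaves 5 − 3 = 2 starred between-arm results that are exposed: defecations and distension.

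**Step 5: the primary outcomes.** The Figure 3 legend gives intubation in 7/40 = 17.5% of controls and 3/40 = 7.5% of the intervention arm, a difference of 10 percentage points, with no p-value. Fisher's exact test on these counts gives p = 0.31 two-sided and 0.16 one-sided. (The plan specifies a log-rank test; this only indicates the strength of the evidence.) Deaths were 7/40 and 1/40. Knowledge of the arm hardly affects whether a death is recorded, although care before death could differ.

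**The case against.** The strongest reply is that silence is not denial. The documents do not say that nobody was masked, and one person listed for formal analysis has no investigation or data-curation role. This stands. A reader might infer that blinding was absent at every level, analysis included; the documents do not support that. They support impossibility for patients and for the team that treats and collects data, and no more than missing specification for everyone else.

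A second reply is that SAP Item 19b concerns adherence. It speaks of collecting data and names intake times and immediate side effects. It does not say who scores qSOFA, Bristol scale or PHQ-9. This stands as a limit: that the same team recorded the outcomes is an inference. It is a fair one, because no separate assessor appears anywhere and because the bloating that the team records overlaps with the distension outcome. For patient-reported outcomes the inference is not needed, since the patient is the unblinded rater.

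A third reply is that most of the starred results would be no stronger under blinding. For oxygen flow, qSOFA and PHQ-9 this is right: they are changes within one arm and carry little weight as evidence of a treatment effect either way. Nor does anything in the tables show that bias occurred. This limits how much may be claimed about the results, but it does not rescue the label.

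**Conclusion.** The label is wrong for patients and for the research team that gives the NSS and collects data. It is unspecified for anyone else. The exposure covers one primary outcome and seven secondary outcomes, and takes in five of the seven starred results in Table 2-A, of which two are between-arm comparisons. Which outcomes count as exposed is a judgement about susceptibility; no amount of bias can be calculated from the documents.

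A reader might go further and infer that the survival result fails for want of blinding. That does not follow: overall mortality is little open to ascertainment bias, and the remaining route, different care by arm, is possible but not shown. The intubation result is more vulnerable, because unblinded staff may decide differently by arm, and it should carry that caveat.

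The conclusion assumes that no placebo, sham or masking procedure existed outside the two documents. If one did, the plan should describe it. The point should be corrected, but it does not invalidate the design.

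**What to change.** 1. Replace blinded with open-label in protocol section 1, protocol section 8.1 and SAP Item 9.
2. Claim masking of another party, for example an analyst or laboratory staff, only if it was actually done, and then name the party and the procedure.
3. Add to SAP Item 26a a statement that these outcomes were assessed unblinded: progression to intubation, oxygen flow, qSOFA, defecations, distension, Bristol scale, PHQ-9 and post-COVID syndrome. Say that the secondary ones are supportive only, that the intubation result is open to performance bias, and that overall mortality is little open to ascertainment bias.
4. Note beside Table 2-A that the starred oxygen flow, qSOFA and PHQ-9 results are within-group tests. Do not list hydric balance among the outcomes open to expectation bias.

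Asking for an analysis on coded arms would gain little now. The SAP already shows results by named arm, including the survival comparison (log-rank p = 0.027), and four of the five people with analysis roles are also investigators.

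The changes are to wording only. No placebo, extra staff or change in sample size is needed. The downside is a less favourable design label.
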